## Appendix H – Liver Function Monitoring

The guidelines described in this section are intended to enable early detection and action following abnormal liver function test (LFT) results. Any patient enrolled in a clinical study with active drug therapy and reveals an increase of serum aminotransferases (AT) to  $> 3 \times$  upper limit of normal (ULN), or bilirubin  $> 2 \times$  ULN, should undergo detailed testing (including at least alanine aminotransferase [ALT], aspartate aminotransferase [AST], alkaline phosphatase [ALP], and total bilirubin [TBL]) for further evaluation and follow-up. Alerts will be generated by the central lab to inform the investigator, study monitor and study team. Testing should be repeated within 48-72 hours of notification. Patients should be asked if they have any symptoms suggestive of hepatobiliary dysfunction.

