14.3. Clinical Laboratory Data

Summary tables for clinical laboratory data will be performed for double-blind component only.

The results of laboratory assessments, which include CBC, Serum chemistries (sodium, potassium, chloride, bicarbonate, BUN, creatinine, glucose, calcium, magnesium, phosphorus, lactate dehydrogenase (LDH), albumin) will be provided by a central laboratory. All summaries will be based on the standard units provided by the central laboratory.

Descriptive statistics for laboratory values (in SI units) and changes from baseline at each assessment time point will be presented by treatment group for laboratory parameters collected in the study.

To assess potentially clinically significant (PCS) laboratory abnormalities (Table 5), the number and percentage of patients with post-baseline lab values outside a pre-defined range (low or high) or limit of change will be tabulated. Laboratory test values will be considered PCS if they meet the criteria listed in the table. The number and percentage of patients with post-baseline PCS values will be tabulated. The

percentages are to be calculated relative to the number of patients with available non-PCS baseline values and at least one post-baseline assessment. The numerator is the total number of patients with at least one post-baseline PCS value. Shift tables may be presented.

Patient incidence for each abnormality will be calculated based on patients with a baseline value and at least one post-baseline value for criteria requiring baseline or patients with at least one post-baseline value for criteria not requiring baseline. If differential dropout is observed between the two treatment arms, then the exposure adjusted incidence rate EAIR (per 100 patient years at risk) will be calculated regarding each abnormality.

A supportive listing of patients with post-baseline PCS values will be provided including the patient ID, study center, baseline, and post-baseline values. Values from unscheduled time points will not be used in post-baseline analysis but will be listed.

In addition, for serology testing and other lab test (e.g. PT, PTT, Vitamin B₁₂ and folate) will be provided in data listings by patient. Local hemoglobin data will be listed along with prescribed dose adjustment for reference.

Table 5: Range of Potentially Clinically Significant Lab Values

Parameter	SI Unit	Lower Limit	Higher Limit
CHEMISTRY			
Alanine Aminotransferase (ALT)	U/L		≥3 * ULN

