14.3.1. Liver Function Tests

The frequency of the following categories will be summarized and compared across dose level cohorts (for open-label component and OL high-erythropoietin component) or treatment groups (for double-blind component).

- Aminotransferase (i.e. AST ≥ 3x ULN or ALT ≥ 3x ULN) or/and Total bilirubin (TBL) ≥ 2x ULN
- ALT or AST > 8 x ULN

- ALT or AST > 5 x ULN for more than 2 weeks
- ALT or AST > 3 x ULN and international normalized ratio (INR) > 1.5 (if INR testing is applicable/evaluated).
- ALT or AST > 3 x ULN with the appearance of fatigue, nausea, vomiting, right upper quadrant pain or tenderness, fever, rash and/or eosinophilia (> 5%).

A scatter plot of the maximum aminotransferase (i.e., ALT or AST) level against maximum TBL at post-baseline will also be presented with dotted reference lines at 3 x ULN for ALT or AST, and 2 x ULN for total bilirubin. In each plot, TBL will be in the vertical axis. Different dots will be used for roxadustat and placebo.

Individual displays of abnormal Liver Enzymes (ALT or AST \geq 3 x ULN) and Bilirubin parameters (\geq 2 x ULN) with corresponding other liver enzymes and bilirubin values during the treatment periods will be listed. The timepoints for subjects falling into Hy's Law Range (ALT or AST > 3 x ULN, and total bilirubin > 2 x ULN), Cholestasis Range (total bilirubin > 2 x ULN), and Temple's Corollary Range (ALT or AST > 3 x ULN) will be marked.

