14.5. Vital Signs

Blood Pressures and Heart Rate baselines are defined as the mean of values obtained from the last 2 weeks of screening including Day 1 prior to the first dose.

Descriptive statistics for vital signs and their changes from baseline at each visit and at the end of study will be presented.

Vital sign values are potentially clinically significant (PCS) if they meet both the observed value criteria and the change from baseline criteria listed in [Table 6](#) below. The number and percentage of patients with post-baseline PCS values will be tabulated by dose level cohort (for open-label component) /treatment group (for double-blind component). The percentages are to be calculated relative to the number of patients with baseline and at least one post-baseline assessment. The numerator is the total number of patients with at least one post-baseline PCS vital sign value. Shift tables may be presented.

Patient incidence for each abnormality will be calculated based on patients with a baseline value and at least one post-baseline value for criteria requiring baseline or patients with at least one post-baseline value for criteria not requiring baseline. If differential dropout is observed between the two treatment arms, then the exposure adjusted incidence rate EAIR (per 100 patient years at risk) will be calculated regarding each abnormality.

Line plots of mean and mean change from baseline of vital sign parameters over time with the associated standard error will be provided.

A supportive listing of patients with post-baseline PCS values will be provided including the patient ID, study center, baseline, and post-baseline values. Values from unscheduled time points will not be used in post-baseline analysis, but will be listed.

Table 6: Criteria for Potentially Clinically Significant Vital Signs

Vital Sign Parameter	Flag	Criteria*	
		Observed Value	Change from Baseline
Systolic Blood Pressure (mmHg)	High	≥ 170	Increase of ≥ 20
	Low	≤ 90	Decrease of ≥ 20
Diastolic Blood Pressure (mmHg)	High	≥ 110	Increase of ≥ 15
	Low	≤ 45	Decrease of ≥ 15
Pulse Rate (bpm)	High	≥ 120	Increase of ≥ 20
	Low	≤ 50	Decrease of ≥ 20
Weight (kg)	High	-	Increase of $\geq 10\%$
	Low	-	Decrease of $\geq 10\%$

*Except for body weight, a post-baseline value is considered as a PCS value if it meets both criteria for observed value and change from baseline.

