19.3. Data Handling Conventions

19.3.1. Analysis Windows

Tables below present the visits assigned for efficacy and safety analyses corresponding to the range of treatment days (window) during which an actual visit may have occurred.

The analysis windows will be only applied to those assessments up to the day before the first week of follow-up visit. Assessments obtained afterwards are considered follow-up assessments. For follow-up assessments, only follow-up assessments on scheduled follow-up visits (i.e. nominal follow-up visits) will be summarized unless otherwise specified.

If more than one assessment is available in the same window, the last assessment is used for analysis. Assessments that do not fall in any windows will not be included in analyses unless otherwise specified. However, all post-baseline assessments will be used for PCS value determination and all assessments will be presented in the data listings.

Table 7.1 Analysis Visit Windows (General)

Analysis Visit	Visit Scheduled Day ^a	Window
Baseline	Day 1	Up to Day 1 Pre-Dose
Week 3	Day 7*(Week # -1)+1	[Day 1 Post-Dose, Scheduled Day +7)
Weeks 5, 7, 9, 11...27	Day 7*(Week # -1)+1	[Scheduled Day -7, Scheduled Day +7)
Week 28 ^b	Day 7*(Week #)+1	[Scheduled Day -7, Scheduled Day +7)
Weeks 31	Day 7*(Week # -1)+1	[Scheduled Day -7, Scheduled Day +14)
Week 35, 39, 43	Day 7*(Week # -1)+1	[Scheduled Day -14, Scheduled Day +14)
Week 47	Day 7*(Week # -1)+1	[Scheduled Day -14, Scheduled Day +21)
Week 52 ^c	Day 7*(Week #)+1	[Scheduled Day -21, Up to Week 4 Follow up)

^a: Relative to the first study medication date. For example, Day 1 = the first dose date of study medication.

^b: Week 28 visit should be conducted at the end of 28 weeks of treatment (2 weeks after Week 27 Visit).

^c: Week 52 Visit should be scheduled at the end of 52 weeks treatment (6 weeks after Week 47 visit).

Table 7.2 Analysis Visit Windows for Lipid Parameters

Derived Visit	Visit Scheduled Day ^a	Window
Baseline	Day 1(first dose day)	Up to Day 1 Pre-Dose
Week 5	Day 7 * (Week # -1) +1	[Day 1 Post-dose, Scheduled Day + 56)
Week 21	Day 7 * (Week # -1) +1	[Scheduled Day - 56, Scheduled Day + 28)
Week 28 ^b	Day 7 * (Week #) +1	[Scheduled Day - 28, Scheduled Day + 35)
Week 39	Day 7 * (Week # -1) +1	[Scheduled Day - 35, Scheduled Day + 49)
Week 52 ^c	Day 7 * (Week #) +1	[Scheduled Day -49, Up to Week 4 follow-up)

^a: Relative to the first study medication date. For example, Day 1 = the first dose date of study medication.

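### SAP 14.3 and 14.5 exclude unscheduled values that 19.3.1 requires for PCS counts, and 14.3.1 does not say which rule its liver categories follow

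*SAP*

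**What the plan says.** Three SAP sections bear on whether an unscheduled safety value is counted.

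- SAP 14.3 (laboratory), after describing the PCS tabulation and its supportive listing: "Values from unscheduled time points will not be used in post-baseline analysis but will be listed".
- SAP 14.5 (vital signs), in the same position: "Values from unscheduled time points will not be used in post-baseline analysis, but will be listed".
- SAP 19.3.1 (analysis windows), after limiting other analyses to values that fall in a window: "However, all post-baseline assessments will be used for PCS value determination and all assessments will be presented in the data listings".

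The PCS count is once per patient. For laboratory data, "The numerator is the total number of patients with at least one post-baseline PCS value". For vital signs, "The numerator is the total number of patients with at least one post-baseline PCS vital sign value".

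SAP 14.3.1, a subsection of 14.3, adds liver categories, including ALT or AST above 8 x ULN and "ALT or AST > 5 x ULN for more than 2 weeks". It also plots each patient's maximum ALT or AST against maximum bilirubin. It does not mention unscheduled values.

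Protocol Appendix H generates such values. After a liver alert, "Testing should be repeated within 48-72 hours of notification". Confirmed abnormalities are then retested two to three times a week, tapering to weekly or less.

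**The concern.** The two rules cannot both be applied to Tables 5 and 6. Because one value is enough to count a patient, the choice of rule can change a patient's status. Two programmers could follow the SAP faithfully and produce different PCS incidences. Under the 14.3 rule, the PCS listing could show a patient whom the PCS table leaves out.

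The liver analyses need maxima and durations. After an alert, those are recorded mainly in repeat samples outside the visit schedule. Carrying the 14.3 exclusion into 14.3.1 would push the liver counts downward, which is the less cautious direction for safety. It could also leave a patient who met the prolonged-elevation criterion in Protocol 4.3 on repeat tests out of the matching SAP category.

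**Working it through.** The plan states no figure for this point, so there is none to reproduce. The check sets the rules side by side and then derives what scheduled tests can show.

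**1. Do the rules cover the same output?** Yes. SAP 19.3.1 names PCS determination. In 14.3 and 14.5 the exclusion directly follows the sentence on the PCS listing, while by-visit statistics are described earlier in each section. Table 5 holds ALT, AST and ALP (at least 3 x ULN) and total bilirubin (above 1.5 x ULN); Table 6 holds vital signs. No precedence is stated.

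**2. Scheduled liver-test days.** Protocol Table 2 gives liver tests at Day 1 and Weeks 3, 5, 9, 13, 17, 21, 25, 28, 39 and 52. SAP 19.3.1 places a visit on day 7 x (week - 1) + 1, except Weeks 28 and 52, which fall on 7 x week + 1.

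| Visit | Day 1 | W3 | W5 | W9 | W13 | W17 | W21 | W25 | W28 | W39 | W52 |
|---|---|---|---|---|---|---|---|---|---|---|---|
| Day | 1 | 15 | 29 | 57 | 85 | 113 | 141 | 169 | 197 | 267 | 365 |
| Gap (days) | – | 14 | 14 | 28 | 28 | 28 | 28 | 28 | 28 | 70 | 98 |

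Subtracting week labels would give 11 and 13 weeks for the last two gaps. The day formula gives 70/7 = 10 and 98/7 = 14.

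**3. The duration category.** Weeks 3 and 5 are exactly 14 days apart, which is not more than 2 weeks. From Week 5 the smallest gap is 28 days. With on-time visits, two scheduled values can therefore show the category only if both are high at least 28 days apart. Visit windows (Protocol 6.5) move this slightly: Weeks 3 and 5 could be up to 14 + 1 + 1 = 16 days apart.

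**4. Illustration of scheduled coverage.** Assume visits on time, an elevation lasting D days, and onset equally likely on any day from Day 2 to Day 366 - D. A gap of g days hides g - D onset days when g > D, so the share with no scheduled test during the elevation is the sum of (g - D) over such gaps, divided by (365 - D).

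- D = 7: (2 x 7 + 6 x 21 + 63 + 91)/358 = 294/358 = 82%.
- D = 14: (6 x 14 + 56 + 84)/351 = 224/351 = 64%.
- D = 28: (42 + 70)/337 = 112/337 = 33%.
- D = 56: (14 + 42)/309 = 56/309 = 18%.

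The share with two scheduled tests more than 14 days apart inside the elevation is 0% for D up to 28. It is 6 x 14/323 = 26% for D = 42 and 6 x 28/309 = 54% for D = 56.

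These shares describe scheduled testing only. They are not the difference between the two rules, because an elevation that no test of any kind catches is absent under both.

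**5. Which Table 5 counts can change?** Appendix H retesting starts at ALT or AST above 3 x ULN, or bilirubin above 2 x ULN. If a scheduled ALT or AST triggered it, that patient already meets the 3 x ULN row and the repeats add nothing there. The count changes only for patients whose first qualifying value was unscheduled. Because the repeat panel also includes ALP and bilirubin, a repeat could be the first to qualify in one of those rows.

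**The case against.** The strongest reply is that the SAP already contains the right PCS rule. The 19.3.1 sentence is an explicit exception and is specific to PCS, whereas 14.3 and 14.5 speak only of post-baseline analysis. A sensible programmer could read the exclusion as applying to by-visit summaries. That reading is reasonable, but the SAP does not state it, and the placement of the two sentences within the PCS text points the other way.

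A reader might infer more than the documents support:

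- **That the SAP discards peak liver values.** It does not say so. SAP 14.3.1 carries no exclusion and asks for maxima; the exclusion reaches it only through its place under 14.3.
- **That the ALT and AST counts in Table 5 are bound to be too low.** Step 5 shows that repeats after a scheduled alert do not alter those rows.
- **That the duration category cannot be judged from scheduled visits.** It can, if two values at least 28 days apart are both high. Scheduled visits are insensitive to it, not blind.
- **That values vanish from the report.** All stay in the listings under either rule. Under Protocol 7.3.7, an abnormality that leads to intervention, or to interrupting or stopping study drug, is also an adverse event.

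Two further limits stand. Patients who stop early have scheduled liver tests at end of treatment, 4 weeks later and then every 8 weeks, which the table above omits. For vital signs, the textual conflict is the same, but Protocol Appendix N sets no repeat schedule like that of Appendix H, so no particular loss can be shown.

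**Conclusion.** The contradiction between 14.3/14.5 and 19.3.1 is certain from the text and should be corrected. Its sure consequence is limited: if 14.3 and 14.5 are followed, patients whose only PCS value was unscheduled drop out of the Table 5 and Table 6 incidences while remaining in the listings.

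The consequence for the liver categories and the plot of maxima is conditional on the exclusion being carried into 14.3.1, where the SAP is silent. In that case the sparse schedule matters: on-time scheduled tests alone could never show more than 2 weeks above 5 x ULN for an elevation of 28 days or less.

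The number of patients affected cannot be computed, because the documents give no count of unscheduled tests. The percentages in step 4 rest on assumed onset, length and on-time visits and are illustrative. The point concerns descriptive safety tables and does not touch the primary efficacy analysis.

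**What to change.** Change three places in the SAP.

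1. In 14.3 and 14.5, limit the exclusion of unscheduled values to by-visit descriptive summaries.
2. In both sections, state that PCS counts use all post-baseline values, scheduled or unscheduled, with a cross-reference to 19.3.1.
3. In 14.3.1, state that every liver category and the maximum ALT/AST-bilirubin plot use all post-baseline values, scheduled or unscheduled.

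The cost is wording only, with no new data. Unscheduled tests go to the central laboratory under Protocol 6.9, so a different assay source is not a general reason to leave them out. The tables and figures listed for the Week 28 analysis in SAP 19.9 include no laboratory or liver table, so none of those needs rework. The downside is that patients sampled more often have more chances to be counted, so abnormality counts may rise slightly; a table footnote can say so.

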14.3.1. Liver Function Tests

The frequency of the following categories will be summarized and compared across dose level cohorts (for open-label component and OL high-erythropoietin component) or treatment groups (for double-blind component).

- Aminotransferase (i.e. AST ≥ 3x ULN or ALT ≥ 3x ULN) or/and Total bilirubin (TBL) ≥ 2x ULN
- ALT or AST > 8 x ULN

- ALT or AST > 5 x ULN for more than 2 weeks
- ALT or AST > 3 x ULN and international normalized ratio (INR) > 1.5 (if INR testing is applicable/evaluated).
- ALT or AST > 3 x ULN with the appearance of fatigue, nausea, vomiting, right upper quadrant pain or tenderness, fever, rash and/or eosinophilia (> 5%).

A scatter plot of the maximum aminotransferase (i.e., ALT or AST) level against maximum TBL at post-baseline will also be presented with dotted reference lines at 3 x ULN for ALT or AST, and 2 x ULN for total bilirubin. In each plot, TBL will be in the vertical axis. Different dots will be used for roxadustat and placebo.

Individual displays of abnormal Liver Enzymes (ALT or AST \geq 3 x ULN) and Bilirubin parameters (\geq 2 x ULN) with corresponding other liver enzymes and bilirubin values during the treatment periods will be listed. The timepoints for subjects falling into Hy's Law Range (ALT or AST > 3 x ULN, and total bilirubin > 2 x ULN), Cholestasis Range (total bilirubin > 2 x ULN), and Temple's Corollary Range (ALT or AST > 3 x ULN) will be marked.

14.4. Excessive Hematopoiesis

The presence of potential EH will be defined if Hb increases by >2.0 g/dL within 4 weeks of treatment during the treatment period. A listing of the patients with potential EH will be provided.

The following summaries will be presented for double-blind component:

- Proportion of patients with potential excessive erythropoiesis.
- Proportion of patients with Hb exceeds 12 g/dl.

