### 3.4.3 Best Supportive Care

Best supportive care including RBC transfusion is permitted to ensure patient's safety. The PI and site staff will utilize their own institutional criteria for the determination of when to transfuse a patient. Use of any ESA (epoetin alfa, epoetin beta, darbepoetin or others) is not permitted (see [Appendix I](#)) and patients who receive an ESA will be discontinued from further treatment with study medication.

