### 6.3.1 Study Procedures and Assessments by Visit

#### 6.3.1.1 Study Procedures and Assessments to be Done at All Study Visits

The following will be done at ALL study visits within the Treatment and Follow-Up Periods:

- Recording of transfusions
- Central CBC with Hb level and WBC differential
- Local hemoglobin level (hemocue device is encouraged but not required)
- Review and record AEs
- Review and record concomitant medications, procedures and non-drug therapies
- Review hemoglobin level for any dose adjustments that are deemed necessary ([Appendix C](#) and [Appendix D](#))
- Ensure patient dosing compliance

Local laboratory testing of Hb for dose adjustment decisions will be done at the Local level – use of the Hemocue device is encouraged but not required. Central laboratory values of Hb will be used for all data analysis purposes

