### 8.1 Sample Size Determination

160 patients are planned to be randomized in a 3:2 ratio to roxadustat or matching placebo. This sample size will provide at least 90% power to demonstrate a statistically significant difference between roxadustat and placebo at the significance level of 0.05 using a two-sided Fisher's test, and assuming the response rates of the primary endpoint are 35% and 5% in roxadustat and placebo, respectively.

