3.2. Sample Size Determination

For the open-label component, the sample size is not determined based on statistical consideration. Up to 24 patients will be enrolled in sequential dose level cohorts. All patients will receive roxadustat in an open-label manner.

For the OL high-erythropoietin component, the sample size is not determined based on statistical consideration. Up to 20 patients will be enrolled in an OL exploratory cohort. All patients will receive roxadustat in an open-label manner.

For the double-blind component, 160 patients are planned to be randomized in a 3:2 ratio to roxadustat or matching placebo. This sample size will provide at least 90% power to demonstrate a statistically significant difference between roxadustat and placebo at the significance level of 0.05 using a two-sided Fisher's test, and assuming the response rates of the primary endpoint are 35% and 5% in roxadustat and placebo, respectively.

In total, approximately up to 204 patients will participate in this study.

Due to the slow enrollment in the double-blind component, an unplanned blinded sample size estimation was performed. Based on this, 120 patients randomized in a 3:2 ratio to roxadustat or matching placebo will provide at least 90% power to demonstrate a statistically significant difference between roxadustat and placebo at the significance level of 0.05 using a two-sided Fisher's exact test, and assuming the response rates of the primary endpoint are 56% and 13% in roxadustat and placebo, respectively. The response rate on roxadustat was based on the response rates from open-label and double-blind components in a blinded fashion. The response rate on placebo was based on the MEDALIST study.

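### The excessive-hematopoiesis summary also counts Hb rises caused by transfusion, which biases the comparison of arms toward showing no excess on roxadustat

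*SAP*

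**What the plan says.** SAP 14.4 defines the event by the size of the Hb change alone: "The presence of potential EH will be defined if Hb increases by >2.0 g/dL within 4 weeks of treatment". For the double-blind component it then reports "Proportion of patients with potential excessive erythropoiesis" and "Proportion of patients with Hb exceeds 12 g/dl", and it promises a listing of the flagged patients. SAP 5.4, 14.3 and 19.3, where a data-handling rule might sit, contain no exclusion, window or flag for Hb values that follow a transfusion.

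Transfusion continues during treatment. Protocol 3.4.3 states that "Best supportive care including RBC transfusion is permitted", on each site's own criteria. It is also documented: "Recording of transfusions" is on the list of procedures for every visit (Protocol 6.3.1.1), and SAP 12.3.1 has all RBC transfusions on the CRF to the end of the study.

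Other parts of the plan do separate transfusion from Hb change. The four-week Hb table in Protocol Appendix D and SAP 19.1 puts anyone transfused in the past four weeks in the row for falling Hb. The Hb-increase endpoint in SAP 12.3.4.4 requires TI of at least 56 days.

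**The concern.** A rise in Hb from donor cells is not hematopoiesis. Every double-blind patient enters on 1 to 4 units per 8 weeks. The one-unit stratum is capped at 30%, so at least 70% come from the 2-4 unit stratum. If roxadustat works as planned, more placebo patients than roxadustat patients go on being transfused, and the placebo proportion is inflated more.

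Excessive erythropoiesis is a risk that the protocol names in its risk-benefit section (2.6). A definition that adds false cases mainly to the control arm makes the drug look safer on this item than it may be. The summary is descriptive, but the two proportions will still be read side by side.

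**Working it through.** SAP 14.4 states no figure, so there is none to reproduce. The check has three steps.

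**1. Direction.** The inputs are the planned response rates. The protocol plans the study "assuming the response rates of the primary endpoint are 35% and 5% in roxadustat and placebo, respectively" (Protocol 8.1). The SAP's re-estimate, for "120 patients randomized in a 3:2 ratio to roxadustat or matching placebo", works "assuming the response rates of the primary endpoint are 56% and 13% in roxadustat and placebo, respectively" (SAP 3.2). Exact Fisher power at these rates is 99.9% for 96:64 and 99.9% for 72:48, consistent with the stated figure of at least 90%.

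The expected non-TI share stands in for being transfused:
- SAP rates: t1 = 1 − 0.56 = 0.44 on roxadustat, t2 = 1 − 0.13 = 0.87 on placebo.
- Protocol rates: t1 = 0.65, t2 = 0.95.
- With the 140 patients reported in SAP 17, split exactly 3:2 as 84:56, the SAP shares give 84 × 0.44 ≈ 37 and 56 × 0.87 ≈ 49 patients. The smaller arm holds more transfused patients.

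Two quantities are assumptions, because the documents give neither:
- d is the true drug-caused rate (zero on placebo).
- q is the share of transfused patients with a transfusion-caused flag, taken as equal in both arms and independent of d.

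Then:
- observed roxadustat = 1 − (1 − d)(1 − t1·q) = d + (1 − d)·t1·q
- observed placebo = t2·q
- observed difference = d − q·[t2 − (1 − d)·t1]

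The bracket is positive for any d at either pair of rates, so any q above zero pulls the difference below d.

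**2. How large q might be.** This used a sawtooth Hb course: a jump at each transfusion, then linear decline. Readings followed the protocol's visit schedule over 28 weeks, with 2 or 4 units per 8 weeks and assumed noise SD 0.3. Share of drug-free patients flagged at least once:
- 0.5-0.7 g/dL per unit: about 0-8%.
- Two-unit episodes at 1.0 g/dL per unit: roughly 16-45%.
- Single-unit episodes: 3% or less.
- With no noise, nobody is flagged. Two units at 1.0 g/dL raise Hb by exactly 2.0, and the rule needs more than 2.0.

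**3. Effect on the summary.** For d = 10% and q = 8% at the SAP rates, roxadustat is 0.10 + 0.90 × 0.44 × 0.08 = 13.2% and placebo is 0.87 × 0.08 = 7.0%. Other values for d = 10%, roxadustat vs placebo:

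| q | TI 56% / 13% | TI 35% / 5% |
|---|---|---|
| 0 | 10.0% vs 0% | 10.0% vs 0% |
| 8% | 13.2% vs 7.0% | 14.7% vs 7.6% |
| 20% | 17.9% vs 17.4% | 21.7% vs 19.0% |
| 30% | 21.9% vs 26.1% | 27.6% vs 28.5% |
| 40% | 25.8% vs 34.8% | 33.4% vs 38.0% |

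The difference reaches zero at q = d / [t2 − (1 − d)·t1]. For d = 10% at the SAP rates this is 0.10 / (0.87 − 0.396) = 21%. For d = 5%, 10%, 15% and 20% it is 11%, 21%, 30% and 39% at the SAP rates, and 15%, 27%, 38% and 47% at the protocol rates.

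**The case against.** The strongest reply is about size. Every break-even value exceeds 8%, so at 0.5-0.7 g/dL per unit the excess on drug stays visible. Even at d = 5% and q = 8% the proportions are 8.3% vs 7.0%, a gap of about 1.4 points that has not reversed. Loss of the signal needs two-unit episodes at about 1.0 g/dL per unit, and in that case the flags come from the assumed noise. This stands.

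Second, TI is a proxy. It means one 56-day transfusion-free window in 28 weeks, and responders may be transfused outside it. Both arms are contaminated, and the imbalance may be smaller than 44% vs 87% suggests. This also stands.

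Third, a reader might infer that the SAP departs from the protocol by dropping a maintenance-phase limit. The documents do not support that as a charge against the definition. Appendix D ties its dosing rule to the maintenance phase, but Protocol 2.6 describes the risk as arising at any time in the treatment period. The passages differ in scope and need reconciling.

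Fourth, there are partial safeguards: the label of potential cases, descriptive reporting (Protocol 8.3.6), the patient listing, and a swimming plot of transfusions (SAP 12.3.1.1). They let a careful reader check individual cases, but they leave the proportions by arm unadjusted. SAP 14.3 leaves unscheduled laboratory values out of its post-baseline analysis. If that applied to 14.4 it would reduce the problem, but scheduled values after a transfusion would remain.

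**Conclusion.** The definition mixes transfusion-caused with drug-caused rises. If placebo patients are transfused more, as the plan expects, the comparison is biased toward no excess on roxadustat. The direction rests on the planning rates, which are not results. The size rests on the rise per unit, episode size, noise and true drug rate, none of which the documents give. Over the ranges shown it runs from slight attenuation to masking. Attenuation is the usual outcome at 0.5-0.7 g/dL per unit, and masking or reversal at d = 10% needs more than about 21% of transfused patients flagged.

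A reader might conclude that the summary will hide or reverse a drug signal; the documents do not support that. Nor do they support treating the Hb >12 g/dL summary as equally affected. It rests on a single value, and entry requires a screening Hb of 10.0 g/dL or less. The change is worth making because the bias has a known direction, the risk is one the protocol names, and the data are in hand.

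**What to change.** In SAP 14.4:

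- Keep the unrestricted proportion by arm.
- Add, by arm, the proportion and exposure-adjusted rate of patients with a rise >2.0 g/dL within 4 weeks and no RBC transfusion between the two Hb values. Limit time at risk to transfusion-free intervals; the rate can follow the pattern of SAP 14.1.2. Without that time at risk, dropping pairs that span a transfusion would lower the count in the more-transfused arm and create a bias the other way.
- Show transfusions in the listing of flagged patients.
- For Hb >12 g/dL, only flag values that follow a transfusion within a stated look-back window, for example the 4 weeks used in SAP 19.1. A condition on two values cannot apply to a single-value threshold.
- Reconcile the scope of the >2.0 g/dL rule: maintenance phase in Protocol Appendix D, any time in the treatment period in Protocol 2.6, SAP 14.4 and the wording of SAP 19.1. No view is taken here on the dosing rule.

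The cost is a little programming on data already on the CRF. The drawback is that drug-driven rises in intervals with a transfusion appear only in the unrestricted row, so the new row supplements that row and does not replace it.
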